8.1.3. Secondary Efficacy Endpoint – Analysis for Overall Survival

Overall survival is defined as the time (months) from the date of C1D1 to the date of death for patients who died in the study due to any cause or the time to the last contact date known to be alive for those patients who survived as of the final database lock for the final analysis (censored cases). OS will not be censored even if a patient receives subsequent anticancer treatments.

The analysis for OS will be based on the FAS.

8.1.4. Secondary Efficacy Endpoint – Myeloprotection Efficacy Endpoints

Secondary myeloprotection endpoints that are defined to assess trilaciclib's effect on multiple lineage protection during the treatment period are described in Table 7 by lineage (i.e., neutrophils, and red blood cells [RBCs]). Endpoints that evaluate trilaciclib's impact on study drug delivery during the treatment period are also described in Table 7.

Unless otherwise specified, all endpoints described in Table 7 are derived based on data collected through scheduled and unscheduled visits during the treatment period.

Lineage	Endpoint	Type of Variable		
Neutrophils	Occurrence of severe neutropenia (during cycles 1/2 and overall study)	Binary		
	Occurrence of febrile neutropenia			
	Occurrence of G-CSF administration	Binary		
RBCs	Occurrence of Grade 3 or 4 decreased hemoglobin	Binary		
Dose Modifications	Occurrence of SG dose reduction	Binary		
	Number of SG dose reductions (event rate per 100 cycles)	Counting		
	Occurrence of cycle delay due to hematologic toxicity	Binary		
	Number of cycle delays due to hematologic toxicity (event rate per 100 cycles)	Counting		

Table 7Myeloprotection Endpoints

G-CSF=granulocyte colony stimulating factor; RBC=red blood cell, SG= sacituzumab govitecan-hziy..

8.1.4.1. Neutrophil-Related Endpoints

Occurrence of Severe Neutropenia (during Cycles 1/2 and overall study)

Occurrence of Severe Neutropenia (Grade 4 neutropenia) for a patient is defined as having as least one ANC value $< 0.5 \times 10^9$ /L among all ANC measurements regardless of scheduled or unscheduled visits. Occurrence of Severe Neutropenia is a binary random variable (Yes or No).

Occurrence of Febrile Neutropenia

FN is an AE as reported by the Investigator and captured in the eCRF. A PT term of FEBRILE NEUTROPENIA is used to identify a FN event. The occurrence of FN for a patient is defined as having at least one FN event and is a binary random variable (Yes or No).

Occurrence and Number of Granulocyte Colony Stimulating Factor (G-CSF) Administrations

Administration of G-CSF is collected throughout treatment period. Cycles where G-CSF was administered will be identified by comparing the start and stop dates of each administration of G-CSF to cycle interval. If any of the time intervals in which G-CSF was administered overlapped with any dates between the start of a cycle and the end of the cycle, that cycle will be considered as having a G-CSF administration. Data handling conventions for missing start and stop dates are described in Section 5.4.

The occurrence of G-CSF administration for a patient is defined as having at least one cycle in which G-CSF was administrated for the patient. It is a binary random variable (Yes or No).

The number of cycles with G-CSF administrations for a patient is the total number cycles where the patient received at least one dose of G-CSF. For patients who did not have any G-CSF use and those who were enrolled but did not receive any study treatment, the value of 0 will be assigned.

8.1.4.2. **RBC-Related Endpoints**

Occurrence of Grade 3 or 4 Decreased Hemoglobin

Occurrence of Grade 3 or 4 decreased hemoglobin (Hgb) for a patient is defined as having at least one Hgb value that was < 8.0 g/dL among all scheduled or unscheduled assessments. It is a binary random variable (Yes or No).

8.1.4.3. Dose Modifications

Occurrence and Number of SG Dose Reduction

The occurrence of a dose reduction for a patient is defined as having at least one dose reduction of SG in a cycle. Occurrence of SG dose reduction is a binary random variable (Yes or No).

Number of SG dose reductions for a patient is defined as the total counts of SG dose reductions. In addition, SG that was permanently discontinued due to toxicity will be also counted as a dose reduction event. The value of 0 will be assigned to those patients who did not have any SG dose reductions. Number of SG dose reductions is a counting random variable and the summary statistics for this variable is event rate per 100 cycles.

Occurrence and Number of Cycle Delays Due to Hematologic Toxicity

Occurrence of cycle delays and the associated reason is collected in detail in the eCRF with the following mutually exclusive categories: Low neutrophil count, Low platelet count, Both low neutrophil count and low platelet count, Other hematologic toxicity, Non-hematologic toxicity, or Other. A cycle that was marked as delayed with the reason of Low neutrophil count, Low platelet count, Both low neutrophil count and low platelet count, or Other hematologic toxicity is considered a delay due to hematologic toxicity.

Occurrence of cycle delays due to hematologic toxicity for a patient is defined as having at least one cycle delay due to hematologic toxicity and is a binary random variable (Yes or No). The number of cycle delays due to hematologic toxicity for a patient is defined as the total number of cycles that were delayed due to such reason for the patient during the treatment period. For patients who did not have any cycle delays due to hematologic toxicity, the value of 0 will be assigned. Number of cycle delays due to toxicity is a counting random variable and the summary statistics for this variable is event rate per 100 cycles.

The analysis of myeloprotection endpoints will be based on the FAS population.

G1 Therapeutics

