# 4.3.3.2. Sacituzumab govitecan-hziy

Per Warnings and Precautions in the prescribing information for sacituzumab govitecan-hziy (Trodelvy Package Insert, 2021), the following are important risks related to sacituzumab govitecan-hziy use:

- Severe or life-threatening neutropenia (boxed warning)
- Severe diarrhea (boxed warning)
- Hypersensitivity and infusion-related reactions, including severe anaphylactic reactions
- Nausea and vomiting
- Patients with Reduced UGT1A1 Activity: Individuals who are homozygous for the *uridine diphosphate-glucuronosyl transferase 1A1 (UGT1A1)\*28* allele are at increased risk for neutropenia, febrile neutropenia, and anemia
- Embryo-fetal toxicity

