# 9.2. Criteria for Starting Cycle 1 and Each Subsequent Dose

Patients must meet all the following criteria to receive study treatment on Cycle 1 Day 1:

- ANC >  $1.5 \times 10^9$ /L
- Platelet count ≥100 × 10^9/L

- Total bilirubin ≤1.5 × ULN
- AST/ALT  $\leq 3 \times ULN$  or  $\leq 5 \times ULN$  in the presence of liver metastasis
- Other nonhematologic drug-related toxicities must be ≤ Grade 1 (except alopecia or peripheral neuropathy that may be Grade 2 or less).

G1T28-213

Patients must also have ANC  $\ge 1.5 \times 10^9 / L$  to receive any Cycle Day 1 dose of study treatment and ANC  $\ge 1.0 \times 10^9 / L$  to receive any Cycle Day 8 dose of study treatment.

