### 12.4.6.3. Analysis of Myelosuppression Endpoints

Myelosuppression endpoints are grouped by lineage and consequence as follows:

- Neutrophils related (including occurrence of SN [during Cycles 1/2 and the overall study], occurrence of FN, and occurrence of G-CSF administration)
- RBC related (including occurrence of Grade 3/4 decrease of hemoglobin, occurrence and number of RBC transfusions on/after Week 5, and occurrence of ESA administration)
- Platelet related (including occurrence of Grade 3/4 decrease of platelets, occurrence and number of platelet transfusions)
- Endpoints related to trilaciclib's effect on dosing or hospitalizations due to chemotherapy-induced myelosuppression (including occurrence and number of dose reductions, or dose delay)

The analysis of myelosuppression endpoints will be based on the FAS.

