7.3. Study Drug Modifications

Study drug modifications will be summarized at the final analysis.

There are three types of study drug modification: dose reduction, cycle delay, and infusion interruption. The number of protocol-permitted dose reductions for each study drug are summarized in Table 5.

Table 5Protocol Permitted Dose Reduction by Study Drug

Study Drug	Number of Dose Reductions Allowed			
Trilaciclib/placebo	0			
Sacituzumab govitecan-hziy	2			

Study drug modifications will be summarized in each of the following categories: chemotherapy dose reduction, treatment cycle delay, and infusion interruption. The number and percentage of patients who had any chemotherapy dose reduction, any cycle delay, cycle delay due to hematological toxicity, or any infusion interruption will be summarized.

In addition, more detailed summaries outlined below will be provided.

Dose reduction for Sacituzumab govitecan-hziv. For Sacituzumab govitecan-hziy, the number and percentage of patients who had at least one dose reduction will be summarized. In addition, the number and percentage of patients will be summarized in the following mutually exclusive categories: "Not Applicable (cycle 1 treatment only)", 0, 1, or 2 reductions for the drug. The primary reason for dose reduction will be summarized.

Cycle delay. Information regarding whether a cycle was delayed was collected in the eCRF for each cycle. The number of cycles that have been delayed will be summarized as a continuous variable. In addition, the number and percentage of patients in each of the following mutually exclusive categories will be summarized: "Not Applicable (cycle 1 treatment only)", 0, 1, 2, …, maximum number of delays.

The reasons for cycle delay collected in eCRF are as follows:

- Low neutrophil count
- Low platelet count
- Both low neutrophil count and low platelet count
- Other hematologic toxicity
- Non-hematologic toxicity
- Other

Patients with reasons entered in the "Other" category will be further classified based on medical review of comments collected on the eCRFs into finer categories as appropriate.

Infusion interruption. Infusion interruption was captured in the eCRF for each study drug with the reasons. Any infusion interruption is defined as infusion interruption of any study drug.

The number of any and trilaciclib infusion interruptions will be summarized descriptively and categorically.

Corresponding data listings will be provided for dose modifications.

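### The SG dose-reduction endpoints listed as myeloprotection measures count reductions for any cause, and their occurrence and number definitions do not agree

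*SAP*

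**What the plan says.** **Purpose.** Protocol 12.4.6.3 groups these measures as "Endpoints related to trilaciclib's effect on dosing or hospitalizations due to chemotherapy-induced myelosuppression (including occurrence and number of dose reductions, or dose delay". SAP 8.1.4 puts them in Table 7 under the myeloprotection endpoints and describes the dose-modification rows as measuring the effect on drug delivery.

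**Reductions.** SAP 8.1.4.3 defines occurrence as follows: "The occurrence of a dose reduction for a patient is defined as having at least one dose reduction of SG in a cycle". For the number it says "Number of SG dose reductions for a patient is defined as the total counts of SG dose reductions", and then "SG that was permanently discontinued due to toxicity will be also counted as a dose reduction event". None of these definitions asks for the reason or limits the toxicity to hematologic events.

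**Delays.** The companion rows of Table 7 are restricted by cause, for example "Occurrence of cycle delay due to hematologic toxicity". SAP 8.1.4.3 accepts only low neutrophils, low platelets, both, or other hematologic toxicity as the reason.

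**Reasons elsewhere.** In SAP 7.3, among the exposure summaries: "The primary reason for dose reduction will be summarized".

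**The concern.** Table 7 treats two paired dosing measures differently. A cycle delayed for diarrhea does not count, but an SG dose reduced for diarrhea does. Severe diarrhea carries a boxed warning for SG (Protocol 4.3.3.2), so this is not a remote cause of reduction, and it is not something protection of the bone marrow addresses.

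SAP Section 10 drops six of the protocol's myeloprotection endpoints. Of the eight rows left in Table 7, four are dosing endpoints and two of those are the all-cause reduction endpoints. In a single-arm study the raw rate is the result: there is no control arm in which the same non-hematologic background would appear and cancel. A reader who takes the reduction rate as evidence about myeloprotection would be reading a mixture.

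**Working it through.** The plan gives no figure for these endpoints, so there is nothing to reproduce. The check compares the definitions.

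**Step 1: what triggers an SG reduction or stop.** Protocol Table 8 has a neutropenia block: prolonged Grade 4 neutropenia, febrile neutropenia, or a neutropenic delay of 2 or 3 weeks. A second block covers Grade 4 non-hematologic toxicity, uncontrolled Grade 3-4 nausea, vomiting or diarrhea, persistent Grade 3-4 non-hematologic toxicity, and non-neutropenic delays. Both blocks lead to reductions. Both also list discontinuation at first occurrence when recovery takes longer than 3 weeks. Protocol 9.3.1 adds that drug-related toxicity requiring either drug to be stopped stops all study drugs.

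**Step 2: score typical patients under SAP 8.1.4.3.**

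| Patient | Occurrence, as written | Number, as written | Due to hematologic toxicity, one rule for both |
|---|---|---|---|
| One reduction, diarrhea only | Yes | 1 | No, 0 |
| One reduction, neutropenia | Yes | 1 | Yes, 1 |
| No reduction; SG stopped for non-hematologic toxicity | Not stated (literally No) | 1 | No, 0 |
| No reduction; SG stopped for neutropenia delaying dosing beyond 3 weeks | Not stated (literally No) | 1 | Yes, 1 |
| Two reductions, then SG stopped for toxicity | Yes | 3 | By recorded reasons |

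Rows 1 and 3 show non-hematologic events entering a myeloprotection endpoint. Rows 3 and 4 show the two definitions disagreeing: number 1, occurrence literally No. In row 4 the literal occurrence endpoint misses an event that was hematologic. Row 5 gives a number of 3, while SAP 7.3 categorizes reductions only as 0, 1 or 2, so the two tables cannot be reconciled for such a patient.

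**Step 3: size per patient.** The final enrollment is 30 (SAP 1.1). If all 30 were dosed and are in the FAS, one misclassified patient moves an occurrence rate by 1/30 = 3.3 percentage points. One extra event moves the number endpoint by 100/C per 100 cycles, where C is the total number of cycles given. The documents do not give C.

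**Step 4: Day 8 doses.** Protocol 9.2 requires an ANC of at least 1.0 × 10⁹/L "to receive any Cycle Day 8 dose of study treatment", and Protocol 9.3 calls a hold at that visit a dose delay, with Cycle 1 Day 8 as its example. The SAP endpoint counts cycles marked as delayed. SAP 7.3 recognizes three kinds of modification (reduction, cycle delay, infusion interruption) and labels patients with only Cycle 1 as not applicable for delay. A Day 8 ANC from 0.5 to below 1.0 × 10⁹/L fails the dosing criterion but is not severe neutropenia (below 0.5 in SAP 8.1.4.1). Whether the resulting hold reaches the delay endpoint depends on how the eCRF delay flag is worded, and the documents do not show that.

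**The case against.** **All-cause reduction is a fair measure of drug delivery, and the SAP calls these rows delivery endpoints.** True, and the all-cause figure should be kept. But on that reading the delay rows should be all-cause too. The SAP restricts one pair and not the other, under a myeloprotection title, and gives no reason.

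**The protocol names dose reductions without a filter.** It does, in the synopsis, in 11.2.2 and in the counting-endpoint text of 12.4.6.3. In the group description quoted above, the words about myelosuppression may attach only to hospitalizations. A reader might infer that the SAP departed from the protocol on reductions and should have listed this in Section 10. The documents do not support that: the SAP follows the protocol's operational wording. The weakness is in the definition and is not an undeclared change.

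**The reasons are already reported.** SAP 7.3 tabulates the primary reason for reduction and provides dose-modification listings, and the FAS and safety population have the same definition. SAP 9.2.3 tabulates AEs leading to discontinuation of any study drug. This narrows the gap. It does not close it, because 7.3 does not describe the toxicity discontinuations added to the count, so the hematologic count cannot be rebuilt from that table alone.

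**The stakes are small.** This stands. The summaries are descriptive, with no test or decision rule, and feed an abbreviated report.

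**Two stronger readings go too far.** A reader might conclude that neither the reduction nor the delay endpoints measure myelosuppression. But the delay endpoints are explicitly hematologic, and the reduction endpoints do include neutropenia-driven reductions. A reader might also conclude that Day 8 holds are certainly left out. That is a reasonable inference, but no text defines a cycle delay or says so. Skipped Day 8 doses do lower relative cumulative dose in SAP Table 4, though without a cause attached.

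**Conclusion.** The point holds for the two reduction endpoints. As written they are all-cause, the number also absorbs SG discontinuation for any toxicity, and so they are not specific to myelosuppression in the way the paired delay endpoints are. The occurrence and number definitions also disagree about discontinuations. Both facts follow from the text and need no assumption.

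The effect is 3.3 percentage points of occurrence per misclassified patient if all 30 were dosed. No total can be given, because the documents contain no SG reduction rate split by cause. The primary PFS analysis is not affected. The Day 8 question is a secondary clarification only: the delay definition is at cycle level and silent on Day 8 holds, while the protocol treats such a hold as a dose delay.

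**What to change.** In SAP Table 7 and 8.1.4.3:

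1. Define occurrence and number of SG dose reductions, and of SG discontinuations for toxicity, as those due to hematologic toxicity by the recorded reason, to match the delay endpoint.
2. Apply the same discontinuation rule to occurrence and to number.
3. Keep the all-cause figures in 7.3 and show them beside the hematologic version. The reason is assigned by the investigator in an open-label study, so the narrower figure carries some judgment.
4. State whether a Day 8 SG dose held or skipped for hematologic toxicity counts in the delay endpoint. The ±1 day allowance in Protocol Section 8 should not be borrowed to define lateness, because it is stated for assessments and not for dosing.

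The cost is SAP wording and one derivation. The reason for reduction is already to be summarized (SAP 7.3), and the reason for stopping study drug is recorded on the eCRF (Protocol 10.1). The SAP lists reason categories only for cycle delays. If the codes for reductions or discontinuations do not separate hematologic causes, the linked AE or a medical review of comments would be needed, as 7.3 already plans for delays coded as other. No dosing rule changes. If the SAP is already signed off, its Section 1 provides for recording the change and its rationale in the CSR.

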# 9.3. Toxicity Management and Dose Modifications

The dose of trilaciclib will not be modified and will remain at 240 mg/m^2 throughout the study. If administration of sacituzumab govitecan-hziy is discontinued, trilaciclib will also be discontinued.

The dose of sacituzumab govitecan-hziy can be reduced, when necessary, as described below. The recommended dose modification procedures for hematologic and non-hematologic toxicities are described in Table 8. If a subsequent cycle is delayed for toxicity, the patient should still complete the clinical laboratory assessments on the scheduled Day 1 (entered as an Unscheduled assessment in electronic data capture [EDC]) as well as on the actual first dosing day of that cycle. If the delay is secondary to hematologic toxicity, weekly repeat hematology assessments should continue until the finding meets criteria for resumption of dosing.

Treatment with sacituzumab govitecan-hziy will be permanently discontinued for a patient in the event of any Grade 4 infusion reactions which occur after pre-medication with antihistamines, H2 blockers, and steroids.

Recommendation for management of trilaciclib AESIs are provided in Table 9. Recommendations for hepatobiliary toxicity management are in Section 9.3.3.

For dose delays due to toxicity, the patient should be followed (at least) weekly, including CBCs if the AE is hematologic, to monitor the toxicity until treatment criteria are met or until they discontinue treatment. A 3-week delay from the scheduled dose of sacituzumab govitecan-hziy is permitted for toxicity and/or administrative reasons. As examples, if at the scheduled Cycle X Day 1 visit (e.g., Cycle 2 Day 1) a dose delay is needed for toxicity reasons, a delay up to 3 weeks from Cycle X Day 1 for sacituzumab govitecan-hziy is permitted; if at the scheduled Cycle X Day 8 visit (e.g., Cycle 1 Day 8) a dose delay is needed for toxicity reasons, a delay up to 3 weeks from Cycle X Day 1 for sacituzumab govitecan-hziy is permitted. Dosing delays >3 weeks from the scheduled dose of sacituzumab govitecan-hziy may be permitted on a case by-case basis with the documented approval of the Investigator and Medical Monitor.

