which delays dosing by 2 or 3 weeks for recovery to		
≤Grade 1		
At time of scheduled treatment, Grade 3-4 neutropenia	First	Discontinue treatment
which delays dosing beyond 3 weeks for recovery to		
≤Grade 1		
Severe Non-Neutropenic Toxicity		
Grade 4 non-hematologic toxicity of any duration	First	25% dose reduction
OR	Second	50% dose reduction
Any Grade 3-4 nausea, vomiting, or diarrhea due to	Third	Discontinue treatment
treatment that is not controlled with antiemetics and		
anti-diarrheal agents		
OR		
Grade 3-4 non-hematologic toxicity persisting >48 hours		
despite optimal medical management		
OR		
At time of scheduled treatment, Grade 3-4 non-neutropenic		
hematologic or non-hematologic toxicity, which delays		
dose by 2 or 3 weeks for recovery to ≤Grade 1		
In the event of Grade 3-4 non-neutropenic hematologic or	First	Discontinue treatment
non-hematologic toxicity, which does not recover to		
≤Grade 1 within 3 weeks		

ANC=absolute neutrophil count; G-CSF=granulocyte colony-stimulating factor

Source: Table recreated from Trodelvy Package Insert, 2021

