4.3. Definitions for Analysis Related Timepoint and Time Interval

Timepoint and time intervals related to efficacy and safety data collected during the treatment period will be summarized. For each specific category of data, the time interval by which the data will be analyzed or summarized will be specified in the respective section in which the data analysis plan is described.

To clarify data inclusion for each time interval of interest and baseline or end values for each given time interval, Table 3 presents definitions for timepoints, timepoint related assessments, and time intervals involved in statistical data analysis or summary.

Table 3Definitions for Timepoints, Timepoint Related Assessments and Time
Intervals

Term	Definition
Start of study (date)	Date of first dose of any study drug
Study baseline (assessment)	The last non-missing value prior to or on the date of the first dose of any study drug at the time that is before the time of the first study drug administration. If the event occurs on the same day as date of first dose of study drug but does not have the exact time captured, the event is assumed to have occurred prior to the first dose of study drug.
Day 1 of Cycle X (date)	The date when the first dose of any study drug for cycle X is administered. Day 1 of Cycle 1 (C1D1) is the same as the start of study.
End of a cycle (date)	It is defined as Day 1 of the subsequent cycle if the cycle is not the last cycle. For the last cycle, it is defined as the date of the End of Treatment Visit (ETV). If the ETV does not occur for a patient, End of the last cycle will be defined as 14 days post the last dose of any study drug.
Duration of a cycle (days)	Total number of days from Day 1 of the cycle to End of the cycle. That is, End of the cycle $-$ Day 1 of the cycle $+$ 1.
Duration of study drug exposure (weeks)	The total number of weeks from Day 1 of Cycle 1 to the End of the last cycle in the study. That is, (End of the last cycle –Day 1 of Cycle $1 + 1$) / 7.
Duration of total follow-up (months)	The total number of months from Day 1 of Cycle 1 to either the date of death or last contact date in the study known alive, inclusive. That is, duration of total follow-up=(date of death or date of last contact date known alive – Day 1 of Cycle $1 + 1$)/30.4375.

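### The hematologic cycle-delay endpoints have no rule for a next cycle that is never given, score Cycle-1-only patients as 0, and include Cycle 1 in the denominator by default, so both lean toward fewer delays

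*SAP*

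**What the plan says.** SAP Table 7 keeps eight myeloprotection endpoints. Two concern cycle delay due to hematologic toxicity: whether it occurred, and how often per 100 cycles. SAP 8.1.4.3 builds both from the eCRF delay item. The counted unit is "A cycle that was marked as delayed with the reason of Low neutrophil count" or one of three other hematologic reasons. Everyone else gets zero: "For patients who did not have any cycle delays due to hematologic toxicity, the value of 0 will be assigned". For the rate it says: "Number of cycle delays due to toxicity is a counting random variable and the summary statistics for this variable is event rate per 100 cycles".

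Five other places bear on this:

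- SAP Table 3 defines Day 1 of Cycle X as "The date when the first dose of any study drug for cycle X is administered".
- Protocol 9.3 has the laboratory tests from a missed Day 1 "entered as an Unscheduled assessment in electronic data capture", not as a visit of the new cycle.
- Protocol Table 8 lists treatment discontinuation for Grade 3-4 neutropenia "which delays dosing beyond 3 weeks for recovery to" Grade 1 or better, with a parallel row for other hematologic toxicity.
- SAP 7.3, summarizing the same delay item as an exposure variable, has a category "Not Applicable (cycle 1 treatment only" that is separate from 0 delays.
- For the neighboring count of dose reductions, SAP 8.1.4.3 adds that "SG that was permanently discontinued due to toxicity will be also counted as a dose reduction event". The delay endpoints have no such sentence.

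**The concern.** A delay that ends in a late dose is counted. A delay that never ends, because counts do not recover and treatment stops, appears to leave nothing to count. In the occurrence endpoint that patient then looks like one whose every cycle began on time. The patients most likely to be missed are those with prolonged cytopenia, which these endpoints are meant to describe.

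Two features push the same way. Patients who received only Cycle 1 enter the occurrence denominator as non-events, although SAP 7.3 treats the question as not applying to them. The rate also spreads delays over cycles that include every patient's first.

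At stake is how well two of the eight Table 7 endpoints describe the data. SAP section 10 drops the platelet endpoints, so cycle delay is the only hematology-specific item left in Table 7 that can register low platelets. Severe neutropenia requires ANC below 0.5 × 10⁹/L, whereas the Table 8 discontinuation row also covers Grade 3.

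**Working it through.** The documents give no expected delay rate, number of stops or mean number of cycles, so there is no plan figure to reproduce. The check applies the scoring rule to cases and then sizes the effect over assumed ranges.

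**1. Scoring rule.** Take a patient who receives Cycle 1, whose counts do not recover, and who then stops.

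- SAP Table 3: Cycle 2 is never dosed, so it has no Day 1.
- SAP 8.1.4.3: no cycle is flagged as delayed, so occurrence is No and the count is 0. The patient adds 0 events over 1 cycle.
- SAP 7.3: the same patient is Not Applicable.

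A patient who starts Cycle 2 on time and has no later delay also scores No and 0. A patient with an earlier flagged delay keeps Yes and the earlier count, and loses only the final event.

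**2. Denominator.** Protocol 12.4.6.3 uses the total treatment period in weeks or cycles. SAP 8.2.4.2 asks for a raw rate per 100 units and excludes nothing. Cycle 1 is therefore included by default, though the SAP never says so explicitly.

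**3. Occurrence.** Take N = 30 (SAP 1.1), assuming all enrolled patients were dosed. Each uncounted stop in a patient with no earlier delay is 1/30 = 3.3 percentage points. If 9 patients have flagged delays (assumed), the plan reports 9/30 = 30.0%. Counting 1, 2 or 3 such stops gives 10/30 = 33.3%, 11/30 = 36.7% or 12/30 = 40.0%.

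**4. Rate, Cycle 1 only.** Let D be flagged delays, C total cycles and m = C/30 the mean cycles per patient. The planned rate is 100·D/C; without Cycle 1 it is 100·D/(C − 30). Their ratio is (C − 30)/C = 1 − 1/m, so including Cycle 1 lowers the rate by 1/m:

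| Assumed m | Lowered by |
|---|---|
| 4 | 25% |
| 8 | 12.5% |
| 12 | 8% |

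**5. Rate, both features.** Let k be the number of next cycles withheld for hematologic toxicity after which treatment stopped. The at-risk rate is 100·(D + k)/(C − 30 + k). With m = 6 and D = 12 (both assumed), C = 180:

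| Version | Calculation | Per 100 cycles |
|---|---|---|
| As planned | 12/180 | 6.67 |
| Without Cycle 1 | 12/150 | 8.00 |
| k = 1 | 13/151 | 8.61 |
| k = 3 | 15/153 | 9.80 |
| k = 5 | 17/155 | 10.97 |

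Over m = 4 to 10, D = 6 to 24 and k = 1 to 5, the at-risk rate is 1.15 to 2.32 times the planned rate. The extremes are 25/271 against 24/300, and 11/95 against 6/120.

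**The case against.** - **The SAP does not state the zero score.** SAP 7.3 says only that delay information was collected for each cycle. A site may have been able to flag a cycle that was due but not dosed. This stands: the gap is a missing rule, and the score of 0 is what the definitions imply in its absence.
- **The route is narrow.** Table 8 is headed as recommendations, and Protocol 9.3 and 10.1 allow longer delays with Investigator and Medical Monitor agreement. A patient who restarts late has a started cycle that can be flagged. This limits how many patients are affected; it does not supply the scoring rule.
- **The stop is reported elsewhere.** It enters the number of SG dose reductions, the reasons for drug discontinuation (SAP 5.1) and the worst-grade hematology table (SAP 9.3.2). It also enters adverse events leading to discontinuation if so recorded, and severe neutropenia if ANC fell low enough. This also stands. A reader might infer that the plan presents the worst hematologic outcome as the best. That holds at most inside these two endpoints, for patients with no earlier flagged delay. The dose-reduction count mixes in non-hematologic toxicity, so it is not a full substitute.
- **All cycles is a legitimate exposure denominator.** The protocol prespecified it, and Cycle 1 is the exposure that can delay Cycle 2. A Cycle 1 Day 8 dose can also be late, and the SAP does not say whether that is a cycle delay. This is a fair reason to keep the all-cycles rate, but not to show it alone when SAP 7.3 already treats Cycle 1 as offering no opportunity for delay.

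**Conclusion.** The point holds as a gap and an inconsistency in the SAP. There is no rule for a next cycle withheld for hematologic toxicity and never given. Cycle-1-only patients are coded two ways, and Cycle 1 is in the denominator by default. On the plain reading both delay endpoints are biased toward fewer delays. Occurrence falls by 3.3 percentage points for each uncounted stop in a patient with no earlier delay, and counting Cycle 1 lowers the rate by 1/m.

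The size in this trial cannot be fixed from the documents. Mean cycles, flagged delays and stops are all assumed, and the zero score assumes that the eCRF delay item sits on started cycles.

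A reader might take this as undermining the trial's statistical conclusions. The documents do not support that: the study is single-arm, these are descriptive secondary summaries, and no test, error rate or power depends on them.

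**What to change.** Amend SAP 8.1.4.3 and align it with 7.3:

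- **Occurrence:** report the percentage in the FAS, and also among patients who started Cycle 2 or had it withheld for hematologic toxicity.
- **Rate:** report per 100 cycles over all cycles, and also over cycles at risk, meaning started cycles from Cycle 2 onward plus next cycles withheld for hematologic toxicity.
- **Events:** count a next cycle withheld for hematologic toxicity, after which treatment stopped, as an event. It must enter both numerator and denominator; otherwise a Cycle-1-only stopper contributes 1 event over 0 at-risk cycles. Show these stops as a separate component, because the number of SG dose reductions already counts toxicity discontinuations and the overlap should be visible.

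The inputs are already collected: the discontinuation reason, and the weekly hematology that Protocol 9.3 requires during a hematologic delay. No dosing or stopping rule changes. The cost is a small extra derivation and slightly less favorable figures; keeping the all-cycles rate beside the new one preserves the prespecified summary.
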